### 3.7.2 INTERIM ANALYSES FOR FUTILITY AND EFFICACY REVIEW

The trial design planned for 4 interim analyses and a final analysis at equally-spaced information points. At each interim analysis cumulative primary outcome data, and potentially the secondary analyses, will be presented to the DSMB. Based on the data, a decision to stop or continue the trial will be taken following the O'Brien-Fleming Rule. If the Z-statistic crosses the lower boundary, the trial will be stopped for futility while if the Z-statistic crosses the upper boundary, the trial will be stopped declaring anticoagulant to be effective in preventing CE. In either case, Stage 1 of the trial will end and secondary analyses, including subgroup analyses will be critical for driving adaptive changes made based on accrued data. Eligibility criteria, efficacy, and safety endpoints will be analyzed at predefined intervals to guide the design of subsequent stages to allow efficient use of data and resources to inform the adaptations in trial design.

Assessments of futility will be conducted at all interim looks, whereas efficacy will only be assessed starting at the third interim analysis (after 60% of the information accumulated; **Table 1**). For the efficacy and futility, O'Brien-Fleming analog alpha-spending function and Hwang-Shih-DeCani beta-spending function will be utilized to create the non-binding boundaries. **Table 1** and **Figure 2** provide specific efficacy and futility boundaries at each interim analysis.

**Table 1:** Stopping Boundaries for Efficacy and Futility based on Z-statistic above.

Look	Information fraction	Efficacy Boundary	Futility Boundary
1	20%	NA	0.1383
2	40%	NA	-0.5933
3	60%	-2.6686	-1.1439
4	80%	-2.2887	-1.5918
Final	100%	-2.0307	-2.0307

**Figure 2:** Stopping Boundaries for Efficacy and Futility based on the Z-statistic described above.

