7.3 Primary Outcome Analysis

The ITT principle will be used for the treatment comparisons of trial outcomes such that subjects randomized to the treatment arms will be included in the analysis. Trial follow up will begin at the time of randomization. In other words, Day 0 is the day of randomization.

As a primary approach, the primary endpoint will be compared between two arms using a two-sample Z-statistic for proportion (standardized difference between proportion having CE in anticoagulant arm and matching placebo arm, positive difference favoring anticoagulant arm). More explicitly, denoting p_P , p_{AA} and p_{PP} the estimated proportion of CE in the whole sample, anticoagulant and placebo group respectively, the null hypothesis of no difference in the proportions will be tested using the test statistic

$$Z = (p_P - p_A) / SE(p_P - p_A),$$

where $SE(p_P - p_A)$ will be estimated by pulling over the two groups, that is

$$SE(p_P - p_A) = \sqrt{p(1-p) \left(\frac{1}{n_P} + \frac{1}{n_A} \right)},$$

where n_P and n_A are the sample sizes for the placebo and anticoagulant groups, respectively.

For Stage 1, the CE rates will also be modeled using a log-binomial regression model with treatment arm as the independent variable and adjusting for trial stratification variables (i.e., antiplatelet use; WHO ordinal scale score). Secondary analyses of this endpoint will include

adjustment for D-dimer levels, patient characteristics, and demographic factors, including race and ethnicity. The matching placebo arm will serve as the “reference group” in this model, and analysis will involve testing whether the coefficient for each active treatment group relative to the reference group is equal to 0, or equivalently, whether the adjusted relative risk for anti-coagulant arm is equal to 1. The adjusted relative risk and the related confidence interval will be provided.

In addition, unadjusted event rates for each treatment group, and relative risk and the absolute risk differences with confidence intervals, will be calculated and presented. Kaplan-Meier cumulative incidence curves will also be presented to allow visualization of the patterns of time to first events. As a sensitivity analysis, a modified intention-to-treat analysis, excluding all randomized participants who fail to initiate treatment, will be conducted.

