7.6.4 Planned Interim Analysis, Futility, and Efficacy

An independent data safety and monitoring board (DSMB) will review all interim analyses prepared by an unmasked statistician. The trial design planned for 4 interim analyses and a final analysis at equally-spaced information points. At each interim analysis cumulative primary outcome data, and potentially the secondary analyses, will be presented to the DSMB. Based on the data, a decision to stop or continue the trial will be taken following the O'Brien-Fleming Rule. If the Z-statistic crosses the lower boundary, the trial will be stopped for futility while if the Z-statistic crosses the upper boundary, the trial will be stopped declaring anticoagulant to be effective in preventing CE. In either case, Stage 1 of the trial will end and secondary analyses, including subgroup analyses will be critical for driving adaptive changes made based on accrued data. Eligibility criteria, efficacy, and safety endpoints will be analyzed at predefined intervals to guide the design of subsequent stages to allow efficient use of data and resources to inform the adaptations in trial design.

Assessments of futility will be conducted at all interim looks, whereas efficacy will only be assessed starting at the third interim analysis (after 60% of the information accumulated; Table 4). For the efficacy and futility, O'Brien-Fleming analog alpha-spending function and Hwang-Shih-DeCanis beta-spending function will be utilized to create the non-binding boundaries. Table 4 and Figure 2 provide specific efficacy and futility boundaries at each interim analysis..

Table 4: Stopping Boundaries for Efficacy and Futility based on Z-statistic above.

| Look | Information proportion | Efficacy Boundary | Futility Boundary |
|-------|------------------------|-------------------|-------------------|
| 1 | 20% | NA | 0.1383 |
| 2 | 40% | NA | -0.5933 |
| 3 | 60% | -2.6686 | -1.1439 |
| 4 | 80% | -2.2887 | -1.5918 |
| Final | 100% | -2.0307 | -2.0307 |

[figure not shown]

Figure 2: Stopping Boundaries for Efficacy and Futility based on the Z-statistic described above

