#### 3.2 KEY SECONDARY AND EXPLORATORY ENDPOINTS

Key secondary endpoints include the following.

1. The composite endpoint of EQ5D index score and mortality at day 30 following randomization
2. The composite endpoint of EQ5D index score and mortality at day 90 following randomization
3. The composite endpoint for the primary outcome at day 45 following randomization
4. The composite endpoint for the primary outcome at day 90 following randomization
5. Composite endpoint of venous thromboembolic events, including symptomatic DVT of the upper or lower extremities, symptomatic and/or clinically relevant PE, and other symptomatic venous thrombosis, including cerebral sinus and splanchnic vein thrombosis at day 30
6. Composite endpoint of arterial thromboembolic events, including symptomatic ischemic stroke, myocardial infarction, and other symptomatic arterial thromboembolic events at day 30

Secondary endpoints will be formally tested using a fallback approach (see Section 4.3) only if the primary endpoint was statistically significant at the two-sided 5% level.

Exploratory endpoints include the following.

1. All-cause mortality at day 30 following discharge from the hospital
2. All-cause re-hospitalization at day 90 following discharge from the hospital

Table 1. Summary of important questions of interest and related estimands

Row	Question of Interest	Objective Description / Study Population	Endpoint	Intercurrent Events/Strategy to handle	Population Summary Estimands
1	Does Apixaban reduce the rate of venous and arterial thromboembolic outcomes, and all-cause mortality during 30 days after discharge?	Primary Objective of the Study / All Randomized Participants	Composite endpoint (CE) of venous and arterial thrombotic complications—including new, symptomatic proximal, or distal DVT of the upper or lower extremities, PE, and new thrombosis of other veins (including cerebral sinus and	The only intercurrent event will be patient drop-out. The drop-out is expected to be less than 5% and un-related to treatment and their data up to the time of drop-out will be	The difference in the proportion of CE between the Apixaban arm and the placebo arm. A negative value will favor the

			splanchnic veins), ischemic stroke, myocardial infarction, other arterial thromboembolism (e.g., mesenteric or acute limb ischemia), and all-cause mortality by day 30	used in the event determination*	Apixaban arm.

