If safety issues arise, the DSMB will use their clinical and statistical judgment to assess the potential risks relative to the potential benefits. The DSMB may also examine the safety and efficacy data in subgroups known to be high risk for bleeding such as those with older age and/or higher BMI. The DSMB will use all available information to make recommendations to the NHLBI. The DSMB can recommend that the Post-discharge COVID-19 trial should continue as proposed, that one treatment arm or more may be dropped, that the trial protocol should be modified, or that the trial should be terminated early for safety reasons. At any of the safety reviews, the DSMB can request a further statistical evaluation of the safety data to make a decision. Only the DSMB and those individuals invited to the DSMB closed session is permitted to examine outcomes by the assigned treatment group. The DSMB will evaluate the rates of the primary endpoint and the safety endpoints by assigned treatment groups overall and within pre-specified subgroups.

[figure not shown]

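### The stopping-boundary table has the opposite sign to the Z-statistic it is meant for, so the interim and final decision rule is wrong as written in both documents

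*SAP*

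**What the plan says.** **The statistic.** Protocol 7.3 and SAP 4.2 both give Z = (p_P - p_A) / SE(p_P - p_A) with a pooled standard error. The direction is also given in words: "matching placebo arm, positive difference favoring anticoagulant arm". A beneficial drug therefore gives Z > 0.

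**The stopping sentence.** SAP 3.7.2, repeated in Protocol 7.6.4, reads: "If the Z-statistic crosses the lower boundary, the trial will be stopped for futility while if the Z-statistic crosses the upper boundary, the trial" is stopped and the anticoagulant declared effective. This agrees with the definition of Z.

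**The boundary table.** The SAP caption is "Stopping Boundaries for Efficacy and Futility based on Z-statistic above". The values are the same in both documents. In Protocol Table 4 the last three rows (look, information, efficacy, futility) are "3 | 60% | -2.6686 | -1.1439", "4 | 80% | -2.2887 | -1.5918" and "Final | 100% | -2.0307 | -2.0307". Looks 1 and 2 have no efficacy bound, and their futility bounds are 0.1383 and -0.5933.

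**The estimand table.** The primary row in SAP 3.2 uses the reverse contrast: "The difference in the proportion of CE between the Apixaban arm and the placebo arm. A negative value will favor the" apixaban arm.

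**The concern.** The definition of Z and the stopping sentence agree with each other, and the table contradicts both. Every efficacy bound is negative and none lies above its futility bound. That is possible only if negative Z favours apixaban. The estimand table uses that direction, but neither document says that the boundaries do, and no visible passage reconciles the two conventions.

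These numbers are the prespecified thresholds for stopping Stage 1. They include the final critical value behind the primary efficacy claim. Under SAP 4.3 that claim gates formal testing of all six key secondary endpoints. SAP 4.3 also makes the form of secondary reporting depend on whether the statistic crossed the efficacy or the futility boundary. Anyone applying the rule must first decide which of the prespecified statements to disregard, possibly with unblinded data in hand.

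**Working it through.** **Inputs.** Placebo rate 4%, risk ratio 0.65 (so apixaban 2.6%), 2,530 per arm, 80% power, two-sided alpha 0.05, looks at 20, 40, 60, 80 and 100% of information (SAP 3.5 and 3.7.2; Protocol 7.2 and 7.6.4). This gives 2,530/5 = 506 per arm per look.

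**1. The absolute values are right.** O'Brien-Fleming-type spending at one-sided 0.025 is α(t) = 2 - 2Φ(z/√t), with z = Φ⁻¹(1 - 0.0125) = 2.2414. At t = 0.6, 2.2414/0.7746 = 2.894, so α = 0.0038. With no efficacy test at looks 1 and 2, the look 3 bound is Φ⁻¹(1 - 0.003808) = 2.6686. Numerical integration, ignoring futility because the bounds are non-binding, gives 2.6686, 2.2887 and 2.0307. Cumulative alpha is 0.0038, 0.0122 and 0.0250. These are the table's efficacy values without the minus sign. Hwang-Shih-DeCani beta spending with β = 0.20 gives futility bounds of -0.138, 0.593, 1.144 and 1.592 on a benefit-positive scale, which is the printed column with every sign reversed. The documents do not state gamma; +1 was inferred because it fits.

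**2. Where the written Z falls under the planned benefit.** The pooled rate is 0.033, so at the final look

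E[Z] = 0.014 / √(0.033 × 0.967 × 2/2,530) = 0.014/0.005023 = +2.79.

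Multiplying by √t gives +1.25, +1.76, +2.16, +2.49 and +2.79 at the five looks. The printed efficacy bounds lie on the other side of zero. At look 1 the chance of being at or above the printed futility value is Φ(1.2466 - 0.1383) = 0.866 by normal approximation.

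**3. Simulation.** Binomial outcomes, pooled-SE Z as in SAP 4.2, 1,000,000 trials per scenario.

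*Reading A: written Z against the labelled columns* (efficacy if Z ≤ the efficacy bound, futility if Z ≥ the futility bound).

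| True rates, placebo vs apixaban | Declared effective, futility followed | Declared effective, futility ignored |
|---|---|---|
| 4.0% vs 2.6% (planned benefit) | 0.000 | about 0 |
| 4.0% vs 4.0% (null) | 0.018 | 0.025 |
| 2.6% vs 4.0% (assumed harm) | 0.684 | 0.789 |
| 4.0% vs 6.15% (assumed harm, RR 1/0.65) | 0.858 | 0.934 |

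Under the planned benefit, cumulative futility stopping is 0.878, 0.992, 0.9997 and 1.000 at looks 1 to 4.

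*Sign made consistent (-Z against the same table).* The planned benefit is declared effective in 0.683 with futility followed and 0.789 with it ignored; the null gives 0.018 with futility followed. The gap between 0.683 and 0.789 comes from following the futility stops, not from the sign.

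*Reading B: the lower/upper sentence applied to the printed numbers.* From look 3 the upper value is the one in the futility column. For a null drug P(Z ≥ -1.1439) = Φ(1.1439) = 0.874 by normal approximation. Simulation gives 0.873 declared effective at look 3, 0.952 by look 4 and 0.980 by the final look. This assumes no stop at looks 1 and 2, where only one bound is printed. If that single value were treated as the lower bound and followed, only about P(Z ≥ 0.1383) = 0.445 of null trials would pass look 1. The false-efficacy rate would then be at most roughly that, still far above 0.025.

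**4. Near-zero results.** Reading A and the consistent rule agree when |Z| is small. At look 1 this region is very narrow. With 33 events in 1,012 participants, a one-event difference gives |Z| = (1/506) / √(0.0326 × 0.9674 × 2/506) = 0.177, already beyond 0.1383.

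**The case against.** The best defence is that no competent team would apply the table in reverse, and several points support it.

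- The column headings, the estimand direction and the need for efficacy bounds to be more extreme than futility bounds leave one sensible reading.
- The bounds are non-binding, and SAP 3.7.1 provides that "The DSMB will evaluate the rates of the primary endpoint and the safety endpoints by assigned treatment groups overall".
- SAP 3.5 reports that simulated type I error and power were adequate. A reversed rule would have had almost no power, so the rule that was simulated was very likely oriented correctly.
- Protocol 7.1 mentions a separate SAP for the DSMB, not available here, which may hold the operational rule.
- The primary test is two-sided, so |Z| ≥ 2.0307 at the final look does not depend on sign, and the reported risk ratio would show the direction.
- In the SAP the formula comes after the boundary table, so the caption's reference is looser there than in the Protocol.
- Readings A and B are two different misapplications. Neither is the plan's single stated rule.

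Much of this stands. The error would probably be caught, and the percentages describe what literal application would do, not what is expected to happen. None of it corrects the text, however. SAP 3.7.2 contradicts itself through its own sentence and table, even if the caption does not reach the formula in SAP 4.2. Verification under SAP 3.10 checks outputs for consistency with the plan, so it cannot settle which part of the plan is right. The two-sided argument helps only at the final look and does not make the printed negative efficacy threshold correct for the defined Z.

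**Conclusion.** The concern holds, and the text must be corrected. The boundary table in both documents has the wrong sign for the Z-statistic and stopping sentence that accompany it. The fault is one of orientation only: the absolute values reproduce, and with signs made consistent one-sided type I error is 0.025 when futility is ignored.

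Applied literally by column heading, with futility followed, the rule stops the planned benefit as futile in 88% of trials at look 1 and 99% by look 2. It declares a harmful drug effective in 68% to 86%. Applied by the lower/upper sentence from look 3, it declares a null drug effective in 87% at look 3 and 98% by the final look. Under the null, Reading A gives 1.8% false efficacy, the same as the correct sign.

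These figures assume 2,530 per arm with equally spaced looks. The harm rates are assumed scenarios, not figures from the plan. Figure 2 is not visible in the copy reviewed, so its orientation is unknown.

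**What to change.** Adopt one convention in both documents, by either route.

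(a) Keep Z = (p_P - p_A)/SE and the stopping sentence, and negate every table value. Efficacy at looks 3, 4 and final becomes +2.6686, +2.2887 and +2.0307. Futility at the five looks becomes -0.1383, +0.5933, +1.1439, +1.5918 and +2.0307. State the inequalities: efficacy if Z ≥ the efficacy bound, futility if Z ≤ the futility bound, with efficacy taking precedence at equality at the final look. Add a note that the estimand table refers to p_A - p_P.

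(b) Keep the boundary and estimand tables, redefine Z as (p_A - p_P)/SE with negative favouring apixaban, and reverse the lower/upper sentence: efficacy if Z ≤ the efficacy bound, futility if Z ≥ the futility bound.

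Under either route, check Figure 2 and the separate SAP for the DSMB against the chosen direction. Route (a) changes two boundary tables and adds a note; route (b) changes the definition of Z, including its stated direction, and one sentence in each document. Alpha, sample size and trial operations are unaffected.

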### 3.8 DATA SOURCES

Initial data collection is the responsibility of the clinical trial staff under the supervision of the site PI. The investigator is responsible for ensuring the accuracy, completeness, legibility, and timeliness of the data reported. Follow-up data will be collected electronically from the participant's self-report and by study staff via telephone. Responsibility for the accuracy, completeness, and timeliness of data collected by telephone is under the supervision of the Coordinating Center investigators at Duke Clinical Research Institute and the University of Illinois-Chicago who are responsible for ensuring the accuracy, completeness, legibility, and timeliness of the data reported.

Copies of the electronic CRF (eCRF) will be provided for use as source documents and maintained for recording data for each participant enrolled in the study. Data recorded in the eCRF derived from source documents should be consistent with the source documents or the discrepancies should be explained and captured in a progress note and maintained in the Coordinating Center's official electronic study record.

Programmed computer edit checks will be run against the database to identify discrepancies and verify the reasonableness of the data. Queries to resolve discrepancies will be generated and resolved by the sites. Analysis datasets will be created by the Data Coordinating Center for the production of tables, figures, and listings. All planned reporting will be based on the analysis datasets, but in the case of emergent safety data, some reporting may occur from the raw eCRF data. All programs written to create analysis datasets and perform analyses will be validated according to Standard Operating Procedures established by the ACTIV4C Data Management and Statistical Analyst teams.

### 3.9 SOFTWARE PACKAGE

The statistical analyses described in this SAP, as well as the production of tables, listings, and figures, will be performed using SAS®, version 9.4 or higher (SAS Institute, Cary, NC) or R software. Additional statistical software may be used as needed.

### 3.10 VERIFICATION OF RESULTS

All tables, listings, and graphs will be verified and reviewed before being considered final. The verification process will ensure that the numbers are produced by a statistically valid method and that the execution of the computations is correct. Qualified statisticians or statistical programmers employed at the Data Coordinating Center who have not been previously involved in the production of the original programming will perform the verification procedures. Methods of verification include independent programming, prior to issuance of the draft statistical report, of all analysis datasets and comparison to data listings. Tables, listings, and figures will be reviewed for accuracy, consistency with this analysis plan, consistency within tables/listings/figures, and consistency with the corresponding output. Once verification is complete, all documentation of the verification process will be saved.

### 3.11 SUBJECT DISPOSITION

The disposition of subjects (number randomized, number who received any amount of the randomly assigned treatment, number completing study drug administration, number who withdrew consent or discontinued from study drug early, and number lost to follow-up, and number who completed the trial) will be summarized by treatment group. The number of subjects screened for inclusion and a breakdown of reasons for exclusion will be summarized. The timing and reasons for early discontinuation of study drug and/or withdrawal from the study will be summarized by treatment group. For the calculation of percentages, subjects who die will not be included in the denominators for visits/assessments beyond their death. Treatment compliance (e.g., number of subjects with missed doses) will be summarized by treatment group. A subject listing of analysis population eligibilities will be generated. A listing of all subjects discontinued from the study after enrollment, broken down by site and treatment group will be provided. The listing will include the reason for discontinuation, treatment group, duration of treatment, and whether or not the blind was broken. Also, for subjects who discontinued from the study after enrollment, a listing of adverse events will be provided. Subject-specific protocol deviations will be summarized by the reason for the deviation, the deviation category, treatment group, disease severity, and (separately) site for all subjects. All subject-specific protocol deviations and non-subject-specific protocol deviations will be included in listings.

